5.2.2 Urine Pharmacokinetics

Urine will be collected continuously for 24 hours post dosing. A sample of urine will also be collected within 2 hours prior to dosing. Urine samples for PK will be pooled into four periods: pre-dose, 0-4 hours post dose, 4-12 hours, and 12-24 hours. Urine samples will be analyzed for concentrations of Scopolamine. Urine samples may also be analyzed for metabolites of Scopolamine.

5.3 COVARIATES

In general, covariates are not applicable for this study, with the exception of PK analysis. The influence of the dose of Scopolamine will be evaluated in various analyses including the PK dose-response relationship, with sex included as a covariate. Sex is valid as a covariate in models of PK parameters based on plasma concentrations, as males typically have higher plasma volumes per unit body mass than females.

6. STATISTICAL METHODOLOGY AND ANALYSES

6.1 GENERAL CONSIDERATIONS

The first and second objective of this study will primarily be addressed through descriptive statistics of safety and PK data. Hypothesis testing and interval estimation will be limited. Specific hypotheses are detailed in 6.3 and interval estimation in 6.4. All data analyses and statistical testing will be conducted using SAS Version 9.4 or Stata version 15 or higher.

6.2 CHANGES FROM PROTOCOL SPECIFIED ANALYSES

Changes to the protocol specified analyses that are made prior to unblinding the data will be noted in a revised protocol and be approved by study sponsor, statistician, and ethical review committee. Upon approval, such analyses will be incorporated into the final SAP. The results of analyses not specified in the protocol but specified in the SAP prior to unblinding will be included in the final statistical report/and or CSR as “additional analyses”.

Changes to the protocol-specified analyses made after unblinding of the data will be considered as “post-hoc”. Post hoc analyses will not be included in the protocol amendments or the final SAP. In the final statistical report/and or CSR, post hoc analyses will be presented separately and subsequent to all analyses specified in the final protocol.

No interim analyses are planned. DSMB and [REDACTED] safety reviews are planned and do not constitute an interim analysis or changes from protocol-specified analyses.

No graphs/figures will be produced for final analysis based on discussion and agreement from client Biostatistician.

6.3 HYPOTHESES AND DECISION RULES

As the objective of this study is to characterize the safety and tolerability of escalating doses of Scop HBT, three sets of safety endpoints will be compared statistically between placebo and active dosing groups. Some PK parameters will also be compared statistically across dose levels. Table 7 describes the hypothesis testing pre-specified in the statistical analysis.

The null hypothesis of no worse scores for Injection Site VAS (pain, itching, tingling, numbness); change in BPRS Score (6 hours, 48 hours, 8 days); change in DSST (48 hours, 8 days); and C-SSRS (SD 8) between dose levels of active Scop HBT and placebo will be tested statistically using a one-sided alternative of worse (higher for C-SSRS, VAS, and BPRS, lower for DSST scores for Scop HBT vs. placebo). Each dose level will be tested against the same placebo group (all participants receiving placebo). Methods for analysis of neuropsychiatric scales and injection site reactions are described in Sections 6.13.4 [6.14.6](#) and [6.14.8](#), respectively.

For PK parameters, variation across doses will be tested for T_{max} , $t_{1/2}$, V_d/F , Cl_F , and MRT against the null hypothesis of no difference across doses. A joint significance test (1 test per parameter) will be used.

Dose-proportionality will be tested using the dose-normalized parameters $C_{max}/Dose$ and $AUC_{\infty}/Dose$. A likelihood ratio test will be used for testing the joint null hypothesis of equivalence across all doses using a two-sided alternative. Each dose level will also be tested against the next dose level using a two-sided test. The methods for analysis and hypothesis testing are described in Section - [6.15](#). A total of 110 hypothesis tests will be performed. Procedures for multiple comparisons are detailed in Section [6.8](#).

Table 7: Pre-Specified Hypothesis Tests

Drug Characteristic	Null Hypothesis	Relevant Endpoints [Count]	Number of Comparisons Per Parameter	Total Number of Hypothesis Tests
Safety	Equivalence with Placebo	Injection site VAS (pain, itching, tingling, numbness) x (10-45 minutes, 1-5 hours, 8-48 hours) [12] Change in BPRS score from baseline (6 hours, 48 hours, SD 8) [3] Change in DSST scores from baseline (48 hours, SD 8) [2]	5 (Each dose level vs. Placebo)	90
Safety	Equivalence with Placebo	C-SSRS (SD 8) [1] Change in DSST scores from baseline (48 hours, SD 8) [2] Proportion with lower raw DSST scores compared to baseline (48 hours, SD 8) [2]	1 (All dose levels vs. Placebo)	5
PK Dose-Equivalence	Equivalence across doses	T_{max} , $t_{1/2}$, V_d/F , MRT, Cl_F	1 Joint Test	5
PK Dose-Proportionality	Equivalence across doses	$C_{max}/Dose$ $AUC_{\infty}/Dose$	1 (joint test) 4 (each dose vs. next higher dose)	10
Total				110

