5.3.3. Intended Benefit for Subjects

There is no benefit to subjects participating in this study. Payment for participation in this study is not a benefit and should not be presented as such. However, potential subjects can be told that study results may provide information required for the marketing of a new or improved product. Results of this clinical investigation will inform follow-on animal efficacy studies and a Phase 2 human clinical study of Scopolamine HBT dosing by confirming the PK upon IM administration.

PK data are key to determining the efficacious dose of Scopolamine HBT for these future studies.

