12.1.1. Pharmacokinetic Analysis

The PK analysis will be performed on the pharmacokinetics analysis set. Blood samples will be obtained for PK assessments prior to dosing and at 2, 5, 10, 15, 20, and 30 minutes and 1, 2, 4, 8, 12, 24, 36, and 48 hours post dose. Scopolamine HBT PK assessments will include

determination of the following parameters: observed C_{max} , T_{max} , V_d , $t_{1/2}$, Cl , AUC_{last} , AUC_{∞} , $C_{max}/Dose$, MRT, and $AUC_{\infty}/Dose$. Plasma concentration time profiles for each subject tested will be evaluated using semi-log plots and characterized using noncompartmental analysis (WinNonlin). PK data will also be summarized graphically by dose group. PK and safety endpoints will undergo PD analysis and evaluation.

Data for PK parameters will be summarized by group using descriptive statistics including mean, standard deviation, minimum, maximum, and may include median and quartiles. All PK data for individual participants will be provided in listings.

Dose proportionality will be tested for $C_{max}/Dose$ and $AUC_{\infty}/Dose$ using ANOVA models. Likelihood ratio tests will be used to test the joint hypothesis of equivalence across dose levels. Equivalence will be tested for each dose level against the next higher dose level. Equivalence of parameters across doses (dose equivalence) will be tested for T_{max} , $t_{1/2}$, V_d , and MRT. All ANOVA models of PK parameters will adjust for sex.

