$$\begin{aligned} \beta_0 &= \beta_0 + \beta_1 \text{ i.e. } \beta_1 = 0 \\ \beta_0 + \beta_1 &= \beta_0 + \beta_2 \text{ i.e. } \beta_1 = \beta_2 \\ \beta_2 &= \beta_3 \\ \beta_3 &= \beta_4 \\ \beta_4 &= \beta_5 \end{aligned} \quad (9)$$

Two PK parameters, C_{\max} and AUC_{∞} , will also be used to test dose-proportionality. ANOVA models will compare C_{\max}/Dose and AUC_{∞}/Dose across active dose levels. Joint significance will be tested using likelihood ratio tests. Individual doses will be compared to the next higher dose using Wald Tests of model parameters.

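### Dose proportionality is assessed only by tests whose null is equality across doses, with no margin and no estimate of how exposure scales with dose, so a non-significant result says little

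*SAP*

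**What the plan says.** Protocol 12.1 and SAP 2 include dose proportionality of Cmax and AUCinf over the dosing range in the PK objective. SAP 6.3 sets the method: "Dose-proportionality will be tested using the dose-normalized parameters" (Cmax/Dose and AUCinf/Dose), with a joint test in which "A likelihood ratio test will be used for testing the joint null hypothesis of equivalence across all doses using a two-sided alternative". It adds: "Each dose level will also be tested against the next dose level using a two-sided test". Table 7 of the same section enters "Equivalence across doses" in the null-hypothesis column.

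Protocol 12.1.1 matches: "Likelihood ratio tests will be used to test the joint hypothesis of equivalence across dose levels", and "Equivalence will be tested for each dose level against the next higher dose level". SAP 6.15.1 gives the mechanics, an ANOVA adjusted for sex, with "Individual doses will be compared to the next higher dose using Wald Tests of model parameters".

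Three other provisions bear on the point. SAP 5.2.1 plans descriptive statistics by cohort and dose, including 95% CIs, and geometric means for AUCinf and Cmax. SAP 6.1 says both objectives rest mainly on descriptive statistics and that testing and interval estimation are limited. It refers to SAP 6.4 for interval estimation, and that section covers only toxicities and serious events.

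**The concern.** The plan uses the word equivalence for what is an ordinary null of equal means. In a real equivalence assessment the null is a departure beyond a stated margin, and the data have to rule it out. Here equality is presumed and the data have to overturn it. With 6 to 9 active subjects per dose, non-rejection can reflect proportionality or too few subjects, and the p-value cannot tell these apart.

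The joint test spreads its 4 degrees of freedom over all patterns and ignores dose order. The adjacent-dose tests compare doses only 1.27- to 1.57-fold apart. Neither yields the quantity a later reader would want: the rate at which exposure changes with dose, and its uncertainty. Protocol 5.3.3 says that "PK data are key to determining the efficacious dose of Scopolamine HBT for these future studies", so a conclusion of proportionality that rests on a weak test could be carried forward with more confidence than the data give.

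**Working it through.** **The plan's own figures.** SAP 3.5 gives an 80% chance of at least one event: 1 − (1 − 0.235)^6 = 0.7996, and 1 − (1 − 0.182)^8 = 0.7995. SAP 6.8 gives the first five Benjamini-Hochberg thresholds: 0.20 × i/110 = 0.0018, 0.0036, 0.0055, 0.0073, 0.0091. Both reproduce. Neither concerns proportionality, for which no power or precision is stated.

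**Inputs from the documents.** Doses 0.005, 0.007, 0.011, 0.014 and 0.021 mg/kg (adjacent ratios 1.40, 1.57, 1.27, 1.50; overall 4.2); n = 6 to 9 active per dose; sex as covariate; alpha 0.05.

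**Assumptions.** Log-normal exposure, a log-linear departure, and a CV of 30–70%. The documents give no CV. Protocol 5.2.2 quotes Cmax 0.68 ± 0.45 ng/mL and AUC 0.94 ± 0.52 h·ng/mL, tied to a 99% CI. If the ± values are CI half-widths from 6 subjects (n assumed), the CVs are about 40% and 34%. If they are SDs, the CVs are 0.45/0.68 = 66% and 0.52/0.94 = 55%.

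**Joint test.** A drift of R-fold in dose-normalised exposure over the range corresponds to an exponent b with b − 1 = ln R / ln 4.2. That is 0.405/1.435 = 0.2825 for 1.5-fold and 0.693/1.435 = 0.483 for two-fold. The sum of squares of ln(dose) about its mean is 1.277. With σ² = ln(1 + CV²), the noncentrality is λ = n × 1.277 × (b − 1)² / σ², and power comes from the noncentral F with 4 and 5n − 6 df.

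Example, n = 6, CV 40%, 1.5-fold: σ² = ln 1.16 = 0.148; λ = 7.66 × 0.0798 / 0.148 = about 4.1; power 28%, so missed 72%.

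Percentage of trials in which the drift is missed:

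| CV | 1.5-fold, n=6 | 1.5-fold, n=9 | 2-fold, n=6 | 2-fold, n=9 |
|---|---|---|---|---|
| 30% | 54 | 31 | 7 | 1 |
| 40% | 72 | 57 | 29 | 9 |
| 50% | 81 | 71 | 49 | 25 |
| 60% | 85 | 78 | 62 | 41 |
| 70% | 88 | 83 | 70 | 53 |

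If the likelihood ratio test is referred to chi-square without small-sample correction, the 1.5-fold drift is missed less often (41–80% at n=6, 24–77% at n=9). Its true type I error is then 9.6% and 7.7%.

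**Adjacent-dose tests.** Take an exponent of 1.4, which is 4.2^0.4 = 1.78-fold drift over the range, with n = 6 and CV 40%. The noncentrality is 0.4 × ln(ratio) / (σ√(2/n)). For the widest step this is 0.4 × 0.452 / (0.385 × 0.577) = 0.81. Power over the four steps is about 7–12%.

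**Power model for comparison.** The 90% half-width for b is t(0.95, 5n − 3) × σ / √(1.277n). For n = 6, CV 40%: 1.703 × 0.385 / 2.77 = 0.24.

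| CV | half-width, n=6 | half-width, n=9 |
|---|---|---|
| 30% | 0.18 | 0.15 |
| 40% | 0.24 | 0.19 |
| 50% | 0.29 | 0.23 |
| 60% | 0.34 | 0.28 |
| 70% | 0.39 | 0.31 |

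For exponent 1.4 and n = 6, the 1-df slope test has power 95/79/49% at CV 30/40/60%, against 79/53/27% for the joint F test.

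**How tight a range is feasible.** A 0.80–1.25 limit over 4.2-fold means b within 1 ± ln 1.25 / ln 4.2 = 1 ± 0.155, that is 0.84–1.16. With a true exponent of 1, the 90% CI falls inside it in about 1.5% of trials (n=6, CV 30%), 0.02% (n=6, CV 40%) and 12% (n=9, CV 30%).

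**The case against.** The strongest defence is that the decision rule is inferred. No sentence in either document says a non-significant result will be reported as proportional. SAP 6.1 puts descriptive statistics first, and SAP 6.8 calls the trial exploratory. That stands, and the point should not be put as if the plan wrote such a rule. The gap remains: SAP 6.3 is headed as setting decision rules, calls equality equivalence, and offers no other criterion.

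Second, SAP 5.2.1 already gives per-dose means, 95% CIs and geometric means, so a drift may be visible. This is true. But separate intervals for five small groups are not an estimate of how exposure scales with dose, and leave the reader to build one after the fact.

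Third, the size depends on an assumed CV. At CV 30% a two-fold drift is almost always found, and expansion to 9 active subjects helps materially. That is why the range is given. Under Benjamini-Hochberg the working threshold can be stricter or looser than 0.05, depending on how many of the 110 tests are small.

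Fourth, the joint ANOVA has a real merit: it can detect departures that are not log-linear. For a 1.78-fold bump at the middle dose alone (n=6, CV 40%), its power is about 0.65 against 0.03 for the slope test. It should stay.

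A reader might also infer that future dosing rests on extrapolating with the missing exponent. Scaling 0.68 ng/mL by 4.2 gives 2.86 ng/mL at the top dose, and the predicted efficacious Cmax of 16–18 ng/mL in Protocol 7.6.2 is 5.6 to 6.3 times that. The documents do not support this step. The scaling itself assumes proportionality. Protocol 5.2.4 reports a mean subcutaneous peak of 18.81 ng/mL after 0.8 mg, although 0.021 mg/kg is 1.47 mg in a 70 kg subject. No passage says the sponsor will extrapolate in this way.

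**Conclusion.** The concern holds as a fault of method and should be fixed. The only inferential analysis of proportionality tests equality as the null, with no margin and no scaling estimate, so non-significance is not evidence of proportionality. With 6 active subjects per dose, a 1.5-fold drift is missed in more than half of trials at every assumed CV from 30% to 70%. With 9, that is so from CV 40% upward. A two-fold drift is missed about half the time or more only from CV 50% at n=6, or at about 70% at n=9. These figures assume log-normal data, a log-linear departure and an F test at 0.05. For AUCinf the effective n may be lower, because SAP 5.2.1 reports no value for profiles without a terminal log-linear phase.

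It would go too far to say that half the primary objective is lost. The objective in Protocol 6.1 is to characterise PK, and proportionality is one component. No statistical test enters the stopping or DSMB decisions (Protocol 12.3, SAP 6.7.2).

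**What to change.** In SAP 6.3 and 6.15.1, and in step with Protocol 12.1.1:

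- Add a power model, ln(Cmax) and ln(AUCinf) = a + b × ln(dose) + sex. Report b with its 90% CI, and the implied departure in dose-normalised exposure over the range, 4.2^(b − 1), with its CI, as the main proportionality result.
- State that a non-significant ANOVA is inconclusive and is not evidence of proportionality.
- Keep the joint ANOVA as supportive, to pick up departures that are not log-linear.
- If an interpretation range is set in advance, make it wide and label it exploratory. A range of 0.84–1.16 would almost never be met at this sample size. A 0.5–2.0 limit on the ratio over the range (b about 0.52–1.48) exceeds the half-width in every case tabulated above.

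The cost is SAP wording and a few lines of code, with no new data. It should be done before unblinding, since SAP 6.2 labels later changes post hoc. The downside is that the reported conclusion will often be inconclusive.

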6.4 UPPER-BOUND ESTIMATION FOR DLTs & SAEs

As part of the first objective, to characterize the safety and tolerability of Scop HBT IM injection at varying dosages, upper limits for the probability of an event at each dosage will be estimated using data on the occurrence of extreme DLTs, non-extreme DLTs, and SAE.

Dose progression follows rules that require dosing be halted if an extreme DLT or a SAE related to the drug occurs within any cohort. Therefore, the maximum number of extreme DLTs that can occur in a cohort prior to stopping is one. Should one nonextreme DLT occur in the first four participants or two in the first 8 participants, dosing will be halted. If dosing is resumed (upon determination of the PI, DSMB, and sponsor) and a second nonextreme DLT occurs among the first 4 in cohort or 3 total DLTs occur, dosing and enrollment will be halted.

Confidence intervals will be determined using 80% confidence interval, such that there is a 10% probability that the true value exceeds the upper-bound. The Pearson-Clopper interval is the most conservative among the binomial intervals, resulting in the highest upper confidence bounds.

Should no events of any type occur within a cohort, with 6 participants dosed, the 80% confidence interval upper bound for the probability of any event is 0.32. Should one extreme

DLT or SAE occur in any cohort, the upper bound for the SAE/extreme DLT will depend on the number dosed prior to the event occurring. Table 8 shows the upper bounds of confidence intervals based on the number of participants receiving active Scop HBT.

Table 8: Upper-bound estimates of Risk Inferred from Events in Cohort

		Number Receiving Active Scop HBT			
		2	4	6	9 ¹
Event Type	Number of Participants with Event	80% C.I. Upper Bound (Pearson-Clopper Method)			
No Events	0	N/A	N/A	0.32	N/A
Extreme DLT	1	0.95	0.68	0.51	0.37
Nonextreme DLT	1 of first 4 in a cohort, none thereafter	0.95	0.68	0.51	0.37
	2 in the first 8 in a cohort	1.0	0.86	0.67	N/A
	2 of the first 4 in a cohort	1.0	0.86	N/A	N/A
	3 in any cohort	N/A	0.97	0.80	0.60
SAE not already designated as a DLT (except unrelated)	1	1.0	0.68	0.51	0.37

¹If nonextreme DLT occurs in a given cohort, the cohort may be expanded to 12 participants, a maximum of 9 of whom will receive active Scop HBT.

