7.6.1. Safety Criteria for Dose Adjustment or Stopping Doses

For the purposes of determining continued dosing within a cohort or dose escalation to a subsequent planned cohort, stopping rules are based on the emergence of DLTs. Nonextreme and extreme DLTs will be considered related AEs/serious adverse events (SAEs) and will be recorded/reported as such.

Dosing of study drug and study enrollment will be halted (temporarily or permanently) as follows:

- Occurrence of any extreme DLT (dosing and enrollment to be halted immediately; PI, research monitor, PVG physician, and DSMB will review and make a recommendation to the sponsor, which will determine if dosing and enrollment may continue);
- Emergence of a specified number (see [Table 6](#)) of nonextreme DLTs among subjects in a particular dosage group (DSMB will review to determine whether dosing and enrollment may continue);
- Occurrence of an SAE not already designated as an extreme or nonextreme DLT, determined to be possibly, probably, or definitely related to the investigational product; dosing and enrollment to be halted immediately until the DSMB has completed a safety review; and

- Sponsor, DSMB, or PI's clinical judgment warrants stopping based on ongoing review of the safety profile.

The maximum tolerated dose will be the highest dose at which none of the following has been observed:

- An extreme DLT in any one subject;
- A nonextreme DLT in 2 of the first 4 subjects or in 3 subjects at any time; and
- Any SAE, not already categorized as a DLT that is considered to be possibly related, probably related, or definitely related to the study drug.

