12.1.2. Safety Analyses

Safety analysis will include data collected from the safety analysis set. DLT and AE data will be coded using the current MedDRA version at the time of study setup, listed individually (including intervention and outcome), and summarized by system organ class and preferred terms within a body system for each treatment group. Data will be summarized by both event (counting each event regardless of subject) and by subject (counting only one event within each system organ class or preferred term). Serious and/or unexpected AEs will also be discussed on a case-by-case basis.

Changes in pulse rate, systolic and diastolic blood pressure, weight, and respiratory rate will be summarized (mean, median, minimum, maximum, standard deviation) by dose level and time point. Clinical laboratory assessment results will be presented.

Upper bounds of 80% confidence intervals of the true probability of events (extreme DLTs, non-extreme DLTs, and severe AEs) will be estimated from the number of events in each cohort using the Pearson-Clopper method.

Descriptive statistics of BPRS, C-SSRS, DSST, RASS (if conducted), and injection site VAS scores (mean, median, standard deviation, minimum, and maximum) will be presented for each dose level and time point.

Changes in the BPRS score (6 hours, 48 hours, and 8 days) from baseline will be compared between placebo and active dose levels using ANOVA models for each time point. The null hypothesis of no difference between placebo and the active dose will be tested for each dose level using a one-sided alternative hypothesis of higher increases among the participants receiving the active drug than among the placebo group.

Participants have C-SSRS scores of zero at baseline. The proportion of individuals having any increase in their C-SSRS score from zero will be compared for each drug dosage level to the placebo group using Fisher's exact test.

The DSST will be conducted at screening, Day -1, Day 3, and Day 8. Changes from baseline (Day -1) will be compared between placebo and active dose levels using ANOVA models for each time point. Placebo control will help to exclude any remaining practice effects or changes

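### SAP 6.4 gives two competing denominators for the extreme-DLT and SAE upper bound, and rests on a one-event premise that the design does not guarantee

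*SAP*

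**What the plan says.** SAP 6.4 sets out how upper limits on event probability at each dose will be obtained. The interval is Clopper-Pearson with an "80% confidence interval, such that there is a 10% probability that the true value exceeds the upper-bound". From the halting rule the SAP concludes that "the maximum number of extreme DLTs that can occur in a cohort prior to stopping is one". It then states that, should one extreme DLT or SAE occur, "the upper bound for the SAE/extreme DLT will depend on the number dosed prior to the event occurring". The next sentence introduces Table 8 as showing upper "bounds of confidence intervals based on the number of participants receiving active Scop HBT", with columns for 2, 4, 6 and 9 active subjects. Extreme DLTs and SAEs each have a single row, for one event. Nonextreme DLTs have rows for one, two and three events, and SAP 6.4 speaks of dosing being resumed only for them.

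Other sections bear on the same quantity:

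- **Resumption.** Under Protocol 7.6.1 a halt may be temporary. After an extreme DLT a recommendation goes to the sponsor, "which will determine if dosing and enrollment may continue". Protocol 7.6.1.3 and Table 6, SAP Table 3 and SAP 6.7.1 also leave restarting open.
- **Spacing.** Protocol 7.2 doses two sentinel subjects, reviews them at 24 hours, then releases the other six of the first eight with no stated interval between them. SAP 3.6 makes five of those six active.
- **Follow-up.** Protocol 11.4.1 collects AEs and SAEs for 30 days after dosing.
- **Analysis set.** SAP 4.2 runs every safety analysis on everyone who received study medication.
- **Protocol estimator.** In Protocol 12.1.2 the upper bounds "will be estimated from the number of events in each cohort using the Pearson-Clopper method".
- **Precedence.** SAP section 1 says that the SAP prevails where the two differ.

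**The concern.** The sentence on the number dosed before the event fits a cohort that ends at its first extreme DLT or SAE. The documents do not make that certain. If the sponsor restarts dosing, more active subjects are treated at the same dose, and a programmer following the sentence would stop counting before reaching them. One following the column heading of Table 8, or SAP 4.2, would include them. The two give different bounds.

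The one-event premise has a similar gap. With several subjects possibly dosed close together and events collected to Day 30, a second event can arise before a halt takes effect, or after a restart. SAP 6.4 neither describes nor tabulates that case.

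At stake is a reported result. Both documents put upper limits on extreme and nonextreme DLT probability into the safety objective. SAP 6.4 adds SAEs, which the objective does not name; Protocol 12.1.2 names severe AEs instead.

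**Working it through.** **Inputs.** Two-sided 80% interval with 10% in the upper tail, Clopper-Pearson (SAP 6.4). Six to nine active subjects per cohort (SAP 3.4).

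**Formula.** With x subjects having the event among n, the upper bound U solves P(X ≤ x | n, U) = 0.10. Equivalently, U is the 0.90 quantile of Beta(x + 1, n − x), and U = 1 if x = n.

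- x = 0, n = 6: U = 1 − 0.10^(1/6) = 0.319.
- x = 1, n = 2: 1 − U² = 0.10, so U = √0.90 = 0.949.
- x = 1, general n: (1 − U)^n + nU(1 − U)^(n−1) = 0.10.

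**Step 1: reproduce Table 8.**

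| x / n | Table 8 | Recomputed |
|---|---|---|
| 0/6 | 0.32 | 0.319 |
| 1/2 | 0.95 (extreme DLT); 1.0 (SAE) | 0.949 |
| 1/4 | 0.68 | 0.680 |
| 1/6 | 0.51 | 0.510 |
| 1/9 | 0.37 | 0.368 |
| 2/6 | 0.67 (nonextreme only) | 0.667 |

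The method is confirmed. The remaining two- and three-event cells also match. The one exception is the SAE cell for 1 of 2, printed as 1.0; the formula gives 0.949, as in the extreme-DLT row. Putting 20% in the upper tail would give 0.235 for 0/6, so the 10% tail is the one used.

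**Step 2: one event, dosing resumed, no further event.** The literal reading counts active subjects up to and including the one with the event.

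| Event in active subject | Literal bound | All 6 active | All 9 active |
|---|---|---|---|
| 2nd | 0.949 | 0.510 | 0.368 |
| 4th | 0.680 | 0.510 | 0.368 |
| 5th | 0.584 | 0.510 | 0.368 |
| 6th | 0.510 | 0.510 | 0.368 |

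The last column also needs the cohort to be expanded, which the protocol ties to nonextreme DLTs.

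**Step 3: a second event.** If the first event is in the fifth active subject and a second in the sixth, the literal bound is 0.584 and the full-cohort bound for 2/6 is 0.667. For 2/9 the bound is 0.490.

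**Step 4: how likely a second event is.** The documents give no true rates. Assuming 5%, 10% or 20%, with independent subjects all dosed, P(at least 2 of 6) = 1 − (1 − p)^6 − 6p(1 − p)^5 = 3%, 11% or 34%. With nine active subjects the figures are 7%, 23% and 56%.

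**Step 5: what truncation does to coverage.** Take six active subjects dosed one at a time. Use the bound for 1/k if the first event is in subject k, and for 0/6 if there is none. Over true rates from 0.001 to 0.999, the chance that the true rate exceeds the bound peaks at 10.0%; the full-cohort bound also peaks at 10.0%. Stopping the count at the first event therefore keeps the nominal error rate and mainly costs precision.

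**The case against.** A reader might infer that SAP 6.4 leaves out subjects dosed after a restart and counts two events as one. The documents do not go that far:

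- No passage expressly excludes later subjects or caps the numerator.
- The statement about a maximum of one is limited to the period before stopping and to extreme DLTs. For SAEs the one-event premise comes only from the conditional sentence and the single table row.
- Table 8 is headed by number receiving active drug. Its nonextreme row for one event in the first four and none later carries bounds at 6 and 9 active, so it already counts subjects dosed after a halt.
- SAP 4.2 would bring later subjects in, and SAP 6.2 lists no departure from the protocol for this bound. Reporting 0.51 where 2/6 requires 0.67 is thus not something the SAP prescribes.

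There is also tension between the two mechanisms. The large gap at the second active subject needs an early event with others still undosed. Closely spaced dosing or late onset, which makes a second event before the halt easier, also brings the literal denominator near the full cohort.

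The practical reach is limited as well. Protocol 12.3 and SAP 6.7.2 rule out statistical tests for halting, and Protocol 7.6.1 already bars a dose with an extreme DLT or a related SAE from being the maximum tolerated dose.

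All of this stands. It does not remove the sentence, which names a different denominator from the one beside it, in the document that takes precedence.

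**Conclusion.** The point holds as a conflict of wording with a numerical consequence in particular circumstances. SAP 6.4 states a denominator that, read literally, disagrees with Table 8's own basis, with SAP 4.2 and with Protocol 12.1.2. It relies on a one-event premise that neither the restart provisions nor the dosing schedule secures.

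In the resumed case with no further event, the literal bound is 0.95 or 0.68 (event at the second or fourth active subject) where the full cohort gives 0.51, or 0.37 with nine active. That overstates the risk. Where a second event follows a late first one, it can understate it: 0.58 against 0.67. The comparison with Protocol 12.1.2 is direct for extreme DLTs; for SAEs it is one of method only, because that section names severe AEs.

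This rests on dosing being resumed or a second event occurring. If neither happens, nothing changes.

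**What to change.** Replace the sentence in SAP 6.4 with a definition. For each dose and event type, x is the number of active subjects with at least one such event. n is the number of all active subjects dosed at that dose. Both are taken at the final data cut and include subjects dosed after a resumed halt. Remove the statements about the number dosed before the event and the maximum of one as the basis for the bound.

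Label Table 8 illustrative, add rows for two or more extreme DLTs or SAEs (2/6 = 0.67, 2/9 = 0.49), and correct the SAE cell for 1 of 2 to 0.95.

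The cost is SAP wording only. It restores agreement with SAP 4.2 and with the estimator in Protocol 12.1.2, and changes no dosing or stopping rule.
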